Developing and Evaluating In-Home Supportive Technology for Dementia Caregivers
Phase IIB
R44AG059458-03
April 14, 2022

Pre-Screening Procedures:

For Phase IIB, participants will be recruited through caregiver organizations, such as the Alzheimer's Association. Recruitment efforts are aimed at the caregivers of individuals with neurodegenerative disease using three types of materials: (a) flyers, (b) a description of the study that was prepared originally for clinicaltrials.gov, and (c) a recruitment video. The video (approximately 2.5-minutes) describes this research study and introduces the in-home technology system. This video would be accessible in emails or online links provided by our research team to groups/organizations and caregivers who wish to learn more about the study. Caregiver groups/organizations may elect to embed the video link in newsletters, or show the video to interested caregivers who may qualify to participate. All recruitment materials describe the general nature and goals of the research and provide information about what participation involves and monetary compensation. The Berkeley research team is listed as the source for additional information and addressing questions in all materials.

Initial Encounter:

Potential participants will be caregivers of PWD and will be recruited through online listservs of caregivers. Interested caregivers will be directed to an online website to learn more about the study, and complete a screening questionnaire to determine eligibility. Interested caregivers will also give their contact information for enrollment, as well as complete the consent to participate. Once a caregiver has enrolled through the website and been determined as eligible for the study, a member of the Berkeley Psychophysiology Laboratory team will assess the capacity of the PWD to give consent to be in the study. Once PWD consent is obtained either on their own, or through surrogate consent, participants will be sent a link to complete a set of questionnaires. Once patient consent is obtained, People Power will mail the Presence Caregiver system to the caregivers in the active condition for self-installation. People Power will be available to schedule virtual self-installation sessions if caregivers want by email or phone. Additional technical support for the system is available by email and phone during the course of the study.

Caregivers who complete the IIB study in the control condition will be provided with an opportunity at the end of the 6-month study to receive a fully-functioning Presence Care system at no cost if they agree to complete questionnaires for an additional 6-month period (completing questionnaires at 9-months and 12-months). Participation is completely optional and caregivers who decline participation upon receipt of our group's email will not be penalized in any way.

Consent:

Participants will give consent online through the study website. Online consent requires participants to click on a box stating, "By clicking here, I indicate that I have read the above consent form and agree to take part in the research." Individuals receiving care (PWD) are asked to consent to participation as secondary subjects in order for information about them to be used

for research purposes. In order to assess a patient's ability to consent to participation, a member of the research team will conduct a phone conversation with both caregiver and patient. The purpose of this conversation is to provide information about the study (e.g., participation responsibilities, compensation information, etc.) and to assess the PWDs cognitive capacity to consent for themselves using UCLA's "Decision-Making Capacity Assessment Tool." More specifically, a member of the Berkeley research team will determine the PWDs ability to 1) understand relevant study information, 2) ability to appreciate the situation and consequences of the study, 3) ability to rationalize or reason information presented, and 4) ability to make their own decision to participate in the study. If the investigator's evaluation is that the PWD can provide consent (i.e., the answer to questions 8 and 9 on the Assessment Tool are both "yes") the PWD will be asked to complete their own consent form via Qualtrics. If the PWD is judged to have diminished capacity (i.e., the answer to questions 8 or 9 are "no") then the caregiver will be asked to provide surrogate consent if the patient assents. Here, caregivers will be informed to the nature of their decision during the study including patient's participation and decision to participate in certain procedures for the patient in order to ensure that the caregiver will be willing to undertake these on-going responsibilities. In addition, caregivers will be asked to identify a witness who will be willing to provide a bystander signature when they are completing the Self-Certification of Surrogate Decision Maker Form.

Baseline Outcome Assessment:

Once caregivers verbally understand and agree to these responsibilities they will be sent the surrogate consent form for the PWD, the self-certification of surrogate decision maker form, and their own consent form via a Qualtrics link. If the investigator's evaluation is that the PWD can provide consent, the PWD will be asked to complete their own consent form via Qualtrics. Once all forms are completed, a link to the first questionnaire administration will be sent for the caregiver. Identical Qualtrics questionnaires will be sent via email to caregivers in both research conditions at baseline, 3 months, and 6 months. The three sets of questionnaires will be identical, except: (a) the baseline questionnaire will also include a contact information form and "Information about person receiving care"; and (b) the 3-month and 6-month questionnaires will also include questions regarding the usefulness of Presence Care in their homes.

Randomization:

300 caregivers will be randomly assigned to the "active in-home technology" condition of Presence Care and the remaining 100 caregivers will be assigned to the "waiting control" condition. Randomization of participants in each group will be determined by People Power employees after the consent process.

Outcome Measures:

All caregivers—regardless of randomized study condition—complete questionnaires on three separate occasions during this study: baseline, 3-months, 6-months. The four outcome measures

are: (a) Zarit Burden Interview-Short Form, a questionnaire measuring caregiver burden (Zarit, Reever, & Bach-Peterson, 1980). 12 items are rated on 0-4 scale. Range: 0-48. No subscales. Higher scores represent worse outcomes; (b) Center for Epidemiological Studies Depression Scale (CES-D), a questionnaire measuring depression (Radloff, 1977). 20 items are rated on a 0-3 scale and summed (range = 0-60). There are no subscales. Higher scores represent worse outcomes. The clinical cut-off is usually set at a score of 16; (c) Beck Anxiety Inventory (BAI), a questionnaire measuring anxiety (Beck, Epstein, Brown, & Steer, 1988). 20 items are rated on a 0-3 scale and summed (range= 0-60). Higher scores indicate worse outcomes. There are no subscales. A score greater than 36 is considered to be clinically significant; and (d) Satisfaction with Life Scale, a questionnaire measuring overall life satisfaction and well-being (Diener, Emmons, Larsen, & Griffin, 1985). 5 items scored on a 1-7 scale and summed (Range = 5-35). Lower scores indicate worse outcomes. A score of 20 is considered neutral with higher scores considered increasingly more satisfied and lower scores considered increasingly more dissatisfied.

Contact initiated by study staff

After completion of the first questionnaire and successful installation of the system, caregivers randomly assigned to the active condition will be mailed a check of \$100. Qualtrics questionnaires will be sent via email to caregivers in both research conditions at baseline, 3 months, and 6 months. Upon completion of the final questionnaire at 6 months, caregiver participants will be mailed a \$50 check to compensate for their time completing questionnaires. A member of the research team will contact the caregivers to let them know they are welcome to uninstall and dispose of the system, or they may choose to keep any and all sensors, devices, or equipment in their home. For those who choose to keep equipment or devices, they will not be charged any cost and we will end our data collection of any related devices and will not ask that they complete any additional questionnaires regarding their usage of the system, sensors, or equipment (i.e., their participation in this study is complete). Caregivers randomly assigned to the waiting control condition will be mailed a check for \$25 upon completion of the first questionnaire. After completion of the 3 and 6 month questionnaires, caregivers will be mailed a check for \$50 and offered an opportunity to enroll in an additional 6-month study. If they enroll, they will be mailed the Presence Care system for them to self-install and have all sensors activated. They will also be asked to complete the questionnaires at 9-months and 12-months. Following the completion of this additional 6-month study, caregivers will be mailed a check for \$125 for the 9 and 12 month questionnaires, as well as the installation to compensate for their time and effort.

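### Nothing makes randomization or mailing of the system wait for a submitted baseline, so some self-reported baselines could be answered after the arm is known; a baseline-only shift would bias the 6-month change

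*Protocol*

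**What the plan says.** Three steps share one trigger, completed consent:

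- **Baseline link.** Protocol, Initial Encounter: "Once PWD consent is obtained either on their own, or through surrogate consent, participants will be sent a link to complete a set of questionnaires". Baseline Outcome Assessment: "Once all forms are completed, a link to the first questionnaire administration will be sent for the caregiver".
- **Randomization.** Protocol, Randomization: "Randomization of participants in each group will be determined by People Power employees after the consent process". The Design paragraph of the SAP repeats who determines the allocation, without a time.
- **Mailing of the system.** Protocol, Initial Encounter: "Once patient consent is obtained, People Power will mail the Presence Caregiver system to the caregivers in the active condition for self-installation".

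The only steps that wait for a completed first questionnaire are payments. For the active arm: "After completion of the first questionnaire and successful installation of the system, caregivers randomly assigned to the active condition will be mailed a check". For the control arm, a smaller check follows the first questionnaire.

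The SAP (Primary Outcomes) defines the four outcomes as changes over the 6 months. Its Analysis paragraph tests them by repeated measures ANOVA with a group-by-time interaction, time having the levels baseline, 3 months and 6 months.

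**The concern.** A link is sent on consent, but the caregiver decides when to answer it. Meanwhile the supplier may randomize and ship on the same consent. A team that follows the text exactly could therefore receive some baselines after the caregiver has learned the arm, for instance because the system has arrived.

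Caregivers cannot be blinded to having the system, and they rate themselves on burden, depression, anxiety and life satisfaction. Knowing the arm could change the answers either way. Active caregivers might report worse at baseline, which would later look like benefit. Alternatively, hope might improve active answers, or disappointment worsen control answers, and either would hide benefit. Because baseline is one of the outcome levels in the planned test, such a shift goes straight into the estimated change. A baseline answered after assignment cannot be repaired later.

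**Working it through.** **1. What the order of the text supports.**

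| Suggests baseline first | Fits either order |
|---|---|
| Initial Encounter mentions the questionnaire link before mailing | Randomization follows consent, with no reference to the questionnaire |
| The Baseline Outcome Assessment heading precedes Randomization | Mailing follows consent, with no reference to the questionnaire |
| The active-arm payment sentence names the first questionnaire before installation | That sentence requires both but does not order them |
| Only the first form collects contact details: "the baseline questionnaire will also include a contact information form" | "Identical Qualtrics questionnaires will be sent via email to caregivers in both research conditions at baseline, 3 months, and 6 months" |
| Only later forms ask about the system: "the 3-month and 6-month questionnaires will also include questions regarding the usefulness of Presence Care in their homes" | |

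The left column shows likely intent. Neither column contains a rule.

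**2. The SAP's own figure.** The SAP states 0.80 power for a medium effect with N = 400 and gives no number for medium. Taking 0.5 SD (assumption) in a two-sided comparison of 300 with 100: SE = √(1/300 + 1/100) = 0.115 SD, and power = Φ(0.5/0.115 − 1.96) = 0.991. Power of 0.80 corresponds to 2.80 × 0.115 = 0.32 SD. The stated figure is not reproduced on this reading, but nothing below depends on it.

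**3. Bias.** Let sA and sC be the arm-average reporting shifts at baseline, absent at follow-up, and b = sA − sC. The contrast (A6 − A0) − (C6 − C0) then has bias −b, whatever the correlation. A shift equal in both arms cancels. If a fraction k of b persists at both follow-ups, the bias is −(1 − k)b.

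**4. Effect on the planned test, with no true effect.** From the documents: 300 and 100, three time points, 5% level. Assumed: complete data, equal SDs, equal correlation ρ of 0.5, 0.6 or 0.7 between time points. With d the between-arm differences at the three times,

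λ = 75 × Σ(d − mean d)² / (1 − ρ), where 75 = 1/(1/300 + 1/100), with F on 2 and 796 df.

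For d = (b, 0, 0), Σ(d − mean d)² = (2/3)b², so λ = 50b²/(1 − ρ). At b = 0.10 and ρ = 0.5, λ = 1.0.

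| d at 0, 3, 6 months (SD) | ρ = 0.5 | ρ = 0.6 | ρ = 0.7 |
|---|---|---|---|
| 0.02, 0, 0 | 5.3% | 5.4% | 5.5% |
| 0.05, 0, 0 | 6.9% | 7.4% | 8.3% |
| 0.10, 0, 0 | 13.2% | 15.5% | 19.3% |
| 0.10, 0.05, 0.05 (half persists) | 6.9% | 7.4% | 8.3% |
| 0.10, 0.10, 0.10 (all persists) | 5.0% | 5.0% | 5.0% |

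A simulation of 6,000 trials agreed: 12.6% (ρ = 0.5) and 18.7% (ρ = 0.7) for the third row.

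**5. What these shifts require.** If only active caregivers are affected, b = share late × shift per late caregiver:

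- 0.10 × 0.20 SD = 0.02 SD
- 0.25 × 0.20 SD = 0.05 SD
- 0.25 × 0.40 SD = 0.10 SD

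**6. Masking, b = 0.05 SD.** The loss of power depends on the true effect.

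- 0.5 SD at both follow-ups: power falls from 0.996 to 0.986 (ρ = 0.5) or from 0.99998 to 0.9998 (ρ = 0.7).
- 0.25 SD at 3 months and 0.5 SD at 6 months: from 0.979 to 0.947 (ρ = 0.5).
- An effect with exactly 80% power (0.31, 0.28 or 0.24 SD at both follow-ups as ρ rises): to 0.64, 0.62 or 0.59.

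**7. Would the planned summaries reveal it?** The baseline difference has SE 0.115 SD. A two-sided 5% test would flag a 0.10 SD shift in 14% of trials and reaches about 80% only at 0.32 SD.

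**The case against.** The strongest reply is that the text mostly points to baseline first, and that randomizing after consent sets an earliest time, not a place relative to the questionnaire. The reference to both research conditions at baseline may mean only that both arms receive the same forms. This stands as evidence of intent. It does not make the order binding, and the stated trigger for mailing is still consent.

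Second, bias by this route needs caregivers to know their arm when they answer. When they are told may be stated on consent pages that are not part of the available text, so no missing notification rule is claimed. In the visible text, the step that reveals the active arm is the shipment, and an electronic link may well be answered before a parcel arrives. That lowers the likely share of late baselines but does not bound it.

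Third, the larger rejection rates need large inputs: 13–19% requires, for example, a quarter of the active arm answering late, each shifted by 0.40 SD, with none of it persisting. This is correct, and the modest case (0.02 SD) is negligible. The masking loss is likewise small if the true effect is 0.5 SD at both follow-ups.

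A reader might infer that late baselines are planned or have occurred, that any individual's shift biases the result by its full size, or that allocation by the supplier's employees has been misused. The documents support none of these. Only the arm-average difference that does not persist carries through in full, and no figure here rests on who performs the allocation.

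**Conclusion.** The point holds as a gap in a stated procedure that is cheap to close, not as a demonstrated bias. Following the written triggers exactly permits a self-reported baseline after the arm is known, and the planned interaction would carry a non-persistent arm-average difference one for one, with a sign that the documents do not determine. The possible size runs from negligible to a rejection rate of nearly 20% over the assumed range of 0.02 to 0.10 SD. The shift, the share answering late, the persistence and the correlation are all assumptions. Power loss from masking at 0.05 SD runs from about one point or less (true effect 0.5 SD at both follow-ups) to 16–21 points (an effect with exactly 80% power). The change should be made; confidence that the problem matters in practice is medium.

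**What to change.** Amend Initial Encounter, Baseline Outcome Assessment and Randomization in the Protocol to give one order: consent, submitted and time-stamped baseline, randomization, notification of the arm, mailing. Preferably, a computer-generated 3:1 assignment is released automatically when the baseline is submitted.

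For caregivers already enrolled, report baseline, assignment and shipping dates by arm. Only if a material share of baselines followed assignment or shipping, add a supportive comparison of the arms at 3 and 6 months without the baseline, beside the planned test and not in its place. It is unaffected by a baseline-only shift but vulnerable to a persistent one: on the mean of the two follow-ups, SE = √((1 + ρ)/2 × (1/300 + 1/100)) = 0.100 to 0.106 SD, and a persistent 0.10 SD shift makes it reject in 15.5–16.9% of trials, where the planned test stays at 5%. Restricting the analysis to early baselines is not advisable, since that would mainly remove slow responders from the active arm.

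Cost: a short amendment, a change of workflow and, if chosen, set-up of the automatic release. Shipment waits for the baseline. Caregivers who never submit one are not randomized, so somewhat more may need to be screened to reach 400. The date report is possible only if the dates were logged.

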Developing and Evaluating In-Home Supportive Technology for Dementia Caregivers, Phase
IIB
R44AG059458-03
April 14, 2022

Statistical Analysis Plan

Primary Outcomes

All caregivers—regardless of randomized study condition—complete questionnaires on three separate occasions during this study: baseline, 3-months, 6-months. The four outcome measures include changes over the 6-month study period for the following scales: Zarit Burden Interview-Short Form, a questionnaire measuring caregiver burden (Zarit, Reever, & Bach-Peterson, 1980). 12 items are rated on 0-4 scale. Range: 0-48. No subscales. Higher scores represent worse outcomes; Center for Epidemiological Studies Depression Scale (CES-D), a questionnaire measuring depression (Radloff, 1977). 20 items are rated on a 0-3 scale and summed (range = 0-60). There are no subscales. Higher scores represent worse outcomes. The clinical cut-off is usually set at a score of 16; Beck Anxiety Inventory (BAI), a questionnaire measuring anxiety (Beck, Epstein, Brown, & Steer, 1988). 20 items are rated on a 0-3 scale and summed (range= 0-60). Higher scores indicate worse outcomes. There are no subscales. A score greater than 36 is considered to be clinically significant.; and Satisfaction with Life Scale, a questionnaire measuring overall life satisfaction and well-being (Diener, Emmons, Larsen, & Griffin, 1985). 5 items scored on a 1-7 scale and summed (Range = 5-35). Lower scores indicate worse outcomes. A score of 20 is considered neutral with higher scores considered increasingly more satisfied and lower scores considered increasingly more dissatisfied.

Statistical Methods

Design: Caregivers will be randomized into two groups: Active In-Home Technology System and Waiting Control. Subjects will be randomized 3:1. Randomization of participants in each group will be determined by People Power employees. With a total N of 400 caregivers in two conditions and measures repeated three times, a comparison between groups using ANOVA will have .80 power to detect a medium effect size at $p=.05$.

Analysis: Descriptive statistics will be used to summarize all the clinical characteristics and demographic outcomes. These will be summarized overall, by treatment group, by assessment time, and by treatment group and time. Continuous variables will be summarized using means, standard deviations, and ranges. Categorical data will be summarized by number and percent. To evaluate the treatment effects, we will use repeated measures ANOVAs. The other predictors will be treatment group, and time (baseline, 3-months, and 6-months for caregiver outcomes). To evaluate treatment effects, an interaction term between treatment group and time will be included to examine treatment group-related differences in the assessments for each outcome. Each significant interaction will be followed up with paired t-tests to examine treatment differences at each set of time points. Although this study involves 4 outcomes, we do not plan formal multiple comparison adjustments if the results fit a coherent pattern that is consistent with the context of

similar studies. In this case, each result will reinforce the other, rather than detracting from one another, as required by formal multiple comparisons adjustments such as Bonferroni. Conversely, if only one or a very few measures reach statistical significance and their directions and/or magnitudes do not coherently fit with our a prior expectations, then we will note that the result(s) with $p < 0.05$ lack plausibility and could be due to chance, despite meeting the conventional cutoff for statistical significance.

Missing Data: If subjects either cannot or refuse to complete surveys we will use a sensitivity analysis approach in dealing with these missing data by performing analysis with 2 versions of scores: 1) with missing item interpolated using mean replacement by group, and 2) only using responses with 0% missing data. If the results differ for the two approaches, then we will report on the differences.

REFERENCES

Bedard, M., D.W. Molloy, L. Squire, S. Dubois, J.A. Lever, and M. O'Donnell, The Zarit Burden Interview: a new short version and screening version. *Gerontologist*, 2001. 41(5): p. 652-7.

Radloff, L.S., The CES-D scale: A self-report depression scale for research in the general population. *Applied Psychological Measurement*, 1977. 1: p. 385-401.

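### Does the .80 power fail because it counts all 400 randomised caregivers and allows for no loss?

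*SAP*

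**What the plan says.** SAP, Statistical Methods (Design): the randomisation ratio is 3:1. The power claim reads: "a total N of 400 caregivers in two conditions and measures repeated three times, a comparison between groups using ANOVA will have .80 power". The target is described only as medium, at the 5% level. No numeric effect size, standard deviation or between-visit correlation is given, and the ANOVA term behind the .80 is not named.

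Protocol, Randomization: "300 caregivers will be randomly assigned to the" active condition and "the remaining 100 caregivers will be assigned to the" waiting control. Allocation "will be determined by People Power employees after the consent process".

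SAP, Statistical Methods (Analysis): "To evaluate treatment effects, an interaction term between treatment group and time will be included", so the treatment effect is judged by group-by-time over three visits.

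SAP, Missing Data: "If subjects either cannot or refuse to complete surveys", the analysis is run twice, once with mean replacement by group and once "only using responses with 0% missing data". Neither document gives an expected loss rate, an inflation of the sample size, or replacement of lost caregivers.

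**The concern.** The number in the power sentence is the number randomised, so the calculation appears to assume that nobody is lost over six months of emailed questionnaires and a self-installed system. The SAP contradicts that assumption by planning for uncompleted surveys. A standard repeated-measures ANOVA drops a caregiver with any missing visit, and replacing a wholly missing questionnaire with the group mean adds no information about the treatment difference.

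The 3:1 split adds to the worry, because loss from the smaller arm costs more. This sentence is also the only justification given for the sample size. If .80 is the true figure at 400, any loss takes the trial below it, and a reader of a null result might credit the trial with more power than it had.

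**Working it through.** **Inputs.** From the documents: 300 active, 100 control, three visits, alpha .05, power .80. Assumed, because the documents are silent: loss of 10, 20 or 30% in each arm, unrelated to outcome; a medium effect of d = 0.5 or f = 0.25; equal correlation between visits of 0 to .8.

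**1. Can the plan's .80 be reproduced?** For a two-group comparison the noncentrality is d² × n1n2/(n1 + n2). At 300/100 the second factor is 30,000/400 = 75. With d = 0.5, 0.25 × 75 = 18.75, and the F test on 1 and 398 df has power .991, not .80. With f = 0.25, the between-group and interaction tests both exceed .99. Working backwards, .80 corresponds to d = (1.960 + 0.842) × √(1/100 + 1/300) = 2.802 × 0.1155 = 0.32. The stated figure is therefore lower than a conventional medium effect gives, and the unstated inputs may be cautious.

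**2. Taking .80 as exact at 300/100.** The noncentrality that gives .80 is 9.67 (df 2, 796) or 7.89 (df 1, 398). Under a common covariance it scales with n1n2/(n1 + n2), whatever the effect pattern.

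| Analysed | n1n2/(n1+n2) | Power, 2 df | Power, 1 df |
|---|---|---|---|
| 300/100 | 75 | .80 | .80 |
| 270/90 (10% loss) | 67.5 | .754 | .757 |
| 240/80 (20% loss) | 60 | .700 | .707 |
| 210/70 (30% loss) | 52.5 | .637 | .649 |
| 300/80 (20% of controls only) | 63.2 | .724 | .729 |
| 240/100 (20% of active only) | 70.6 | .774 | .775 |

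At the margin, one control lost costs (300/100)² = 9 times the information of one active caregiver lost.

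**3. Taking medium as d = 0.5.** For a two-group comparison at 240/80, noncentrality is 0.25 × 60 = 15 and power is .971. Power reaches .80 only after about 57% of each arm is lost.

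For the 2-df interaction, let v be the group difference at each visit in SD units. The noncentrality is [n1n2/(n1 + n2)] × Σ(v − mean of v)²/(1 − ρ). For v = (0, .25, .5) the sum of squares is .125; for v = (0, .5, .5) it is .167.

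| ρ | v | 300/100 | 240/80 |
|---|---|---|---|
| 0 | (0, .25, .5) | .787 | .685 |
| .3 | (0, .25, .5) | .915 | .841 |
| .3 | (0, .5, .5) | .973 | .932 |
| .5 | (0, .25, .5) | .979 | .943 |
| .7 | (0, .25, .5) | .999 | .996 |

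Of these cases, only zero correlation with a linear effect comes near .80 without loss. Zero correlation is implausible for the same scale answered three times by the same person. In the weakest plausible row (ρ = .3, linear), power at 20% loss is .841; at 30% loss (210/70, noncentrality 52.5 × .125/.7 = 9.375) it is .786.

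**The case for a change.** The strongest reply is that the sentence cannot stand whichever way it is read. A sponsor who means d = 0.5 has the wrong power figure, and one who means .80 must accept that it falls with loss. The slack in step 3 rests on an effect size that the documents never state, so the plan has not earned it. A remote trial should expect loss, and the small control arm is where loss hurts most.

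Much of this stands. The power sentence is under-specified, and a fuller one would give the ANOVA term, effect size, correlation and expected loss. But the shortfall rests on assumptions too: a 20% loss rate that appears nowhere, and an .80 treated as exact although it cannot be reproduced.

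Three parts of the case are weaker. Allocation after consent does not exclude allocation after baseline, so it is only inference that a caregiver with no baseline could count in the 400. The missing-data paragraph speaks of missing items; for a skipped item, mean replacement keeps the caregiver's other answers. And retention has some support: controls who complete are offered a free system (Protocol, Initial Encounter), and payments are tied to questionnaires (Protocol, Contact initiated by study staff). Neither supplies a loss rate.

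The remedies are not compelled either. A 250/150 split does preserve .80 through 20% loss (200 × 120/320 = 75), but gives up 50 active users in a trial meant to develop the technology as well as evaluate it. Keeping 300 active and raising controls to 137, or enrolling 400/0.8 = 500 at 3:1, is simply recruiting more. Naming the interaction as the powered term without recomputing could attach the .80 to a test it was not calculated for, since the sentence speaks only of a comparison between groups.

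**Conclusion.** The observation is correct: the power statement uses the full 400 randomised and shows no allowance for loss. If .80 is exact at 300/100 and 20% of each arm is lost, power is .70 to .71. The inference that the design misses its target is not supported. Under a conventional d = 0.5 with correlations of .3 to .7, power at the same loss is .84 or more for the interaction and .97 for a two-group comparison.

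No change to the plan follows. The missing inputs are a reporting gap in a planning sentence. They do not alter who is analysed, which test is run or how a result is read, and the numbers analysed and the precision achieved will be visible in the data.

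This conclusion rests on reading a medium effect as about half a standard deviation and on loss no heavier than roughly 20% per arm. It would change if the sponsor's own target were near 0.32 SD with material loss expected; nothing in the documents says so.

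### The pooled-error ANOVA on arms of 300 and 100 makes no allowance for unequal spread: its nominal 5% test would run at about 7-9% or 2.5-4% if follow-up SDs differed by 20-30% (assumed); arm-specific variances are a cheap improvement.

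*SAP*

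**What the plan says.** The SAP (Statistical Methods, Analysis paragraph) states: "To evaluate the treatment effects, we will use repeated measures ANOVAs". Treatment is judged by the group-by-time interaction over baseline, 3 months and 6 months, for each of four outcomes. The Design paragraph adds "Subjects will be randomized 3:1" and "With a total N of 400 caregivers in two conditions and measures repeated three times". The protocol (Randomization) puts 300 caregivers in the active arm, and "the remaining 100 caregivers will be assigned to the" waiting control.

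Neither document names a covariance structure, a sphericity correction or a rule for unequal variances between arms. Neither gives an SD or a within-person correlation. The ordinary reading is therefore the standard F test with one pooled error term.

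The active arm installs the system itself (Protocol, Initial Encounter). Its first payment follows the first questionnaire and "successful installation of the system" (Protocol, Contact initiated by study staff).

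**The concern.** The standard interaction F test assumes that both arms share one covariance matrix. Equal arms largely protect the test when that assumption fails; 3:1 allocation removes the protection. The test is too liberal if controls vary more and too conservative if the active arm varies more.

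Each outcome is to be read at p < 0.05, with no formal multiplicity adjustment if the results form a coherent pattern. Each p value therefore has to be calibrated on its own.

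**Working it through.** **Plan's own figure.** The documents give no figure for test size. The nearest is the power claim, "will have .80 power to detect a medium effect size". With 300/100 and d = 0.5 (an assumed reading of medium), the noncentrality is 0.5 × √(300 × 100/400) = 4.33, and two-sided power is 99.1%. Power of .80 corresponds to d ≈ (1.96 + 0.84)/8.66 = 0.32. The claim does not reproduce, but that is a separate matter and nothing below depends on it.

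**Inputs.** From the documents: n = 300 and 100, three waves, p = .05 (two-sided assumed), group-by-time test. Assumed: normal data, no dropout, SD ratios of 1.1 to 1.3, and correlations between waves (baseline-3 months / baseline-6 months / 3-6 months) of .6/.6/.6, .7/.49/.7, .55/.5/.75 and .5/.45/.8 (epsilon 1.0, .875, .873, .784).

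**Step 1: the mismatch.** The pooled variance is (299·v_A + 99·v_C)/398, so the active arm has weight 299/398 = 75%. The true variance of the mean difference is v_A/300 + v_C/100. With v_A = v_C the control share is 0.01/(0.01 + 0.00333) = 75%.

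**Step 2: closed form for the 6-month change.** Size of the pooled test = 2·[1 − Φ(1.96·√(pooled/true))], where pooled is the pooled variance × (1/300 + 1/100).

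Take correlation .6 and equal baseline SDs of 1. The change variance is 2 − 1.2 = 0.80 in an arm whose SD stays at 1. With follow-up SD r it is 1 + r² − 1.2r, which is 1.00 at r = 1.2 and 1.13 at r = 1.3.

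| Wider arm, follow-up SD | pooled | true | size |
|---|---|---|---|
| Control ×1.2 | .01133 | .01267 | 6.4% |
| Control ×1.3 | .01176 | .01397 | 7.2% |
| Active ×1.2 | .01267 | .01133 | 3.8% |
| Active ×1.3 | .01397 | .01177 | 3.3% |

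If the SDs differ by 1.3 at every wave, baseline included, the same formula gives 8.5% (control wider) and 2.6% (active wider).

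**Step 3: the group-by-time F test.** Let d be the arm difference on two orthonormal time contrasts and S the pooled covariance of those contrasts. Then F = d′d / [(1/300 + 1/100)·tr(S)] on 2 and 796 df. Simulated size, 8,000 to 20,000 trials per setting, with ranges over correlation patterns:

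| Wider arm | only follow-up SDs differ | all waves differ |
|---|---|---|
| Control ×1.1 | 6.4-6.7% | 6.5-7.1% |
| Control ×1.2 | 7.0-7.8% | 7.6-9.2% |
| Control ×1.3 | 8.2-9.0% | 9.2-11.0% |
| Active ×1.1 | 3.9-5.1% | 3.5-4.5% |
| Active ×1.2 | 3.2-4.7% | 2.6-3.9% |
| Active ×1.3 | 2.5-3.7% | 2.1-3.0% |

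With equal covariances the size is 4.9-6.2%. Departure from sphericity alone therefore adds only about 0.5 to 1 point.

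**Step 4: would Greenhouse-Geisser repair it?** No. With .7/.49/.7 correlations and all waves scaled, an active/control SD ratio of 0.75 gives 10.8% uncorrected and 9.7% corrected. A ratio of 1.33 gives 2.4% and 2.1%.

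**Step 5: arm-specific covariance.** Estimate the contrast covariance separately as W_A and W_C, and replace the pooled term by A = W_A/300 + W_C/100. The Box-type statistic is d′d/tr(A), with numerator df tr(A)²/tr(A²). Arm-specific interaction tests, of this and a Hotelling-type form, had size 4.3-5.6% in the settings tried; Welch on the 6-month change had 4.5-5.4%.

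**Step 6: power.**
- Arms equal, spherical: interaction .803 vs .796 and .762 vs .753 (pooled vs arm-specific), a cost under 1 point.
- Arms equal, not spherical: a cost of about 2 to 3 points, somewhat more in the least spherical pattern. Part of this is the pooled test's own excess over 5%.
- Welch on the 6-month change, arms equal: .823 vs .822 and .827 vs .823.
- Active follow-up SD ×1.2, effect 0.2 then 0.3 SD: .672 vs .704 and .658 vs .717. The arm-specific test gains about 3 to 6 points, less where non-sphericity is marked.

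**The case against.** The strongest reply is that no material difference in spread is documented. Much of it stands.

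- **No effect on anyone.** Randomised arms then share one outcome distribution (differential dropout aside), and the test runs at about 5-6%. A distorted false-positive rate needs a treatment that changes the spread but leaves the average changes equal. That is possible if some caregivers gain and others are burdened, but it is a narrow null.
- **Baseline.** It precedes treatment, so its SDs are equal in expectation. The follow-up-only column of the table is the realistic one.
- **Mechanism.** If half the caregivers install and gain g SD, independently of their baseline score, the active SD ratio is √(1 + 0.25g²): 1.03 at g = 0.5 and 1.08 at g = 0.8. A ratio of 1.2 needs g = √(0.44/0.25) = 1.33. Mixed uptake alone thus gives a small ratio, and on the conservative side. The installation wording only sets when a payment is sent; it does not report uptake.

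A reader might infer that the test runs anywhere from 2% to 10%. That range needs SDs to differ by about 30% at all waves, baseline included. A reader might also infer that pooling over the three waves is half the problem, but it adds only 0.5 to 1 point. Nor do the documents support saying that all four p values are wrong: that holds only if spreads differ materially. The calculations had no missing data, and the SAP's group-mean replacement itself alters each arm's variance, so nothing here is claimed for every way of handling missing data.

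What remains is that the plan gives no protection, inspecting variances first would make the choice of test depend on the data, and the robust test costs little.

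**Conclusion.** The point holds as a cheap improvement; it is not a demonstrated error. If follow-up SDs differ by 20-30% between arms, the planned 5% interaction test runs at about 7-9% (control wider) or 2.5-4% (active wider, up to 4.7% in one correlation pattern). These figures rest on assumed SD ratios, assumed correlations, normal data and complete follow-up.

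Differences under 10% do little harm. The likelier consequence is lost power, because varied uptake and response would tend to widen the active arm: about 3 to 6 points if its follow-up SD is 1.2 times the control SD. Inflated false positives would need controls to vary more, for example because the worst-off caregivers gain most, and the documents give no basis for expecting that.

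**What to change.** Add one sentence to the SAP's Analysis paragraph: all between-arm tests, and any intervals reported, use variances estimated separately by arm. For the 6-month change, which the SAP's Primary Outcomes section already makes the outcome, use a Welch or sandwich standard error. For any group-by-time F test kept, use a Box-type (ANOVA-type) statistic with arm-specific covariance, which also handles non-sphericity. Fix this in advance, with no preliminary variance test.

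The cost is standard software plus the small power loss shown in Step 6 if the arms' covariances are in fact equal.
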